#### 8.0 Study Withdrawal/Discontinuation

The participant is free to withdraw from the study at any time. He/she should inform the primary investigator or any co-investigator.

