## 9.0 Statistical Considerations

We will attempt to demonstrate clinical improvement of the postinflammatory hyperpigmentation by decreasing the size, intensity, and number of the facial lesions by comparing the treatment side to the control side of the face.

Patients will be evaluated prior to treatment, and at each follow-up visit both 4 weeks, 8 weeks and 12 weeks post-treatment using the Postacne Hyperpigmentation Index (PAHPI). The scoring system is as follows:

Weighted score (S)		Median lesion size
2		<3 mm
4		3-6 mm
6		7-10 mm
8		>10 mm
Weighted score (I)		Median lesion intensity
3	Slightly darker than surrounding skin	
6	Moderately darker than surrounding skin	
9	Significantly darker than surrounding skin	
Weighted score (N)		No. of lesions
1		1-15
2		16-30
3		31-45
4		46-60
5		>60

 Table I. Scoring the postacne hyperpigmentation index

Total postacne hyperpigmentation index = S + I + N; score range: 6-22.

Using power analysis to determine sample size:

In the study by Kim et al, they demonstrated a significant decrease in melasma, another disorder of facial hyperpigmentation, using topical tranexamic acid. They demonstrated a significant decrease in the melasma area and severity index of approximately 33% with a sample size of 23 patients. For our study, a sample size of 25 patients is sufficient to detect a clinically important difference of 30% between treatment and control sides of the face using a two-tailed z-test of proportions between two groups of 80% power and a p-value of 0.05.

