## 11.0 Follow-up and Record Retention

Each participant will be enrolled in the study for 12 weeks with a total of 3 clinic visits. During these 12 weeks, the clinic visits include: 1 visit for initial baseline evaluation, and three follow-up appointments at 4 weeks, 8 weeks and 12 weeks of treatment. All pictures will be stored

securely on the dermatology department password protected hard drive and all data will be deleted at the end of the study.

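### The plan sizes the trial at 25 patients with no allowance for loss, and the only test it names cannot use week-4 and week-8 scores from a patient without a final score

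*Combined protocol and SAP*

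**What the plan says.** The sample-size paragraph in section 9.0 (Statistical Considerations) says that "a sample size of 25 patients is sufficient to detect a clinically important difference of 30% between treatment and control sides of the face". The calculation behind this number is described as "using a two-tailed z-test of proportions between two groups", and its error rates are given as "80% power and a p-value of 0.05". It gives no dropout rate and no inflation step, and does not say whether the 25 are enrolled or evaluable. It also gives no control-side proportion and no rule for turning a PAHPI score (range 6 to 22) into a responder.

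Section 8.0 says "The participant is free to withdraw from the study at any time". It has no rule on replacing a patient who leaves or on using the data already collected. Section 11.0 says "Each participant will be enrolled in the study for 12 weeks". Sections 6.0 and 9.0 have PAHPI followed from baseline through weeks 4, 8 and 12, with one side of each face treated and the other given vehicle. No primary time point, analysis set, repeated-measures method or missing-data rule appears anywhere. The z-test in the sample-size sentence is the only statistical test in the document.

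**The concern.** There are two linked gaps.

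First, 25 is presented as enough for 80% power, yet patients may leave at any point in 12 weeks of daily self-treatment. In a split-face design each departure removes a whole treated-versus-vehicle pair.

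Second, a z-test of two proportions takes one binary result per side at one time. It treats the two sides as independent groups, although they belong to the same face, and it makes no use of the baseline score. If the final visit is the one analysed, a patient scored at weeks 4 and 8 but not at week 12 contributes nothing, although the data exist.

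At stake are power that may be lower than stated, information that is collected and then not used, and possible bias if the patients who stay differ from those who leave in how far the two sides differ.

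**Working it through.** **Inputs from section 9.0.** n = 25 patients, so 25 treated and 25 vehicle sides; difference 30%, read as 30 percentage points because the test is of proportions; two-sided alpha 0.05 (z = 1.960); power 80% (z = 0.8416).

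**Inputs assumed.** Control-side proportion p1, not given, taken over 0 to 0.70, with p2 = p1 + 0.30. Numbers lost, not given, taken as 1 to 5 of 25.

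**Step 1: the plan's figure.** With m = (p1 + p2)/2, A = √[2m(1−m)] and B = √[p1(1−p1) + p2(1−p2)], the required number per side is

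n = [(1.960·A + 0.8416·B)/0.30]².

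At 0.03 versus 0.33: m = 0.18, A = √0.2952 = 0.5433, B = √0.2502 = 0.5002. So n = [(1.0649 + 0.4210)/0.30]² = 24.5, rounded up to 25. The same formula gives 22 at 0 versus 0.30, 24 at 0.02 versus 0.32, 27 at 0.05 versus 0.35, 32 at 0.10 versus 0.40 and 43 at 0.35 versus 0.65. The plan's 25 therefore cannot be reproduced from its stated inputs alone. It comes out exactly only near a control proportion of 0.03, or in the mirror case near 0.67.

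**Step 2: power after loss, on the plan's own test.** Power = Φ[(0.30·√n − 1.960·A)/B]. At 0.03 versus 0.33:

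- n = 25: (1.5000 − 1.0649)/0.5002 = 0.870, power 80.8%
- n = 22: (1.4071 − 1.0649)/0.5002 = 0.684, power 75.3%
- n = 20: (1.3416 − 1.0649)/0.5002 = 0.553, power 71.0%

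Across control proportions:

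| Control vs treated | 25 | 24 | 22 | 21 | 20 |
|---|---|---|---|---|---|
| 0 vs 0.30 | 86.7% | 85.3% | 81.9% | 80.0% | 77.9% |
| 0.02 vs 0.32 | 82.7% | 81.1% | 77.4% | 75.3% | 73.1% |
| 0.03 vs 0.33 | 80.8% | 79.1% | 75.3% | 73.2% | 71.0% |
| 0.05 vs 0.35 | 77.2% | 75.4% | 71.5% | 69.4% | 67.2% |
| 0.35 vs 0.65 | 56.7% | 54.9% | 51.3% | 49.3% | 47.4% |

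(The 80.0% at 21 is 79.96% before rounding, which is why the formula in step 1 returns 22.) The values are symmetric about 0.35, so every control proportion from 0.05 to 0.65 gives less than 80% with all 25 present.

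**Step 3: the 80% does not carry over to a paired test.** For a paired binary comparison (McNemar) with total discordance ψ and d = 0.30, n = [(1.960·√ψ + 0.8416·√(ψ − d²))/d]². This gives 24 at ψ = 0.30, 42 at ψ = 0.50 and 59 at ψ = 0.70 (ψ assumed).

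**Step 4: what the earlier visits can recover.** Suppose 5 of 25 miss week 12 but all have week 8, and the side differences at the two visits correlate at r (both assumed). The effective number of pairs for the week-12 mean is 1/[(1 − r²)/20 + r²/25]:

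- r = 0.5: 1/(0.0375 + 0.0100) = 21.1
- r = 0.7: 1/(0.0255 + 0.0196) = 22.2
- r = 0.8: 1/(0.0180 + 0.0256) = 22.9

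To put this on a power scale, take a paired t-test, two-sided 0.05, with a standardised difference of 0.584. That value is back-solved to give 80% at 25 pairs and is not taken from the plan. Power is then 78.2% at 24 pairs, 74.3% at 22 and 69.8% at 20. The effective pairs above correspond to about 72%, 75% and 76%, against 70% for completers only.

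**The case against.** The strongest reply has four parts.

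*The z-test is not stated to be the analysis.* It appears only in the sample-size sentence, and week 12 is never called primary. A reader might infer that the plan prescribes a week-12 test in completers. The documents do not say so; week 12 is inferred here because it is the last visit. This part stands. But no other analysis is given either, so the gap remains.

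*Power need not fall as soon as one patient leaves.* A reader might infer that 80% is lost with the first withdrawal. Step 2 does not support this: 24 patients still give 85.3% at 0 versus 0.30 and 81.1% at 0.02 versus 0.32. At 0.05 versus 0.35, power is below 80% with nobody lost, so dropout is not the cause there. This part stands as well. Without a control proportion, spare power can be neither claimed nor ruled out.

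*Bias is narrower than it looks.* A withdrawal removes both sides together, so patients who leave because their face as a whole did better or worse do not by that fact distort the side contrast. Bias requires dropout related to the difference between sides.

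*The gain is small and shown at its best.* Step 4 assumes that every lost patient was seen at week 8 and treats the correlation as known. An unstructured covariance would be estimated from about 20 to 25 patients, and patients lost earlier contribute less.

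Section 8.0 is also a statement of the right to withdraw, not a forecast of how many will. None of this supplies the missing allowance or a rule for incomplete follow-up.

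**Conclusion.** The point holds in a limited form. The plan has no allowance for loss, and the only test it names ignores pairing and baseline and cannot use earlier scores from a patient without a final one. The cost in power on the plan's own test depends on the unstated control proportion. Near 0.03, where 25 is the exact requirement, the loss of 3 to 5 patients takes power from 80.8% to between 75.3% and 71.0%. At 0 there is room down to 21 patients. From 0.05 to 0.65 the 80% is not reached even with complete follow-up. The numbers lost are assumed throughout.

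Using the earlier visits recovers the equivalent of about 1 to 3 pairs when 5 of 25 miss week 12, under assumed correlations of 0.5 to 0.8. This is a change the sponsor should make because it is cheap and uses data already planned. It does not show that the trial fails at the first withdrawal or that its result will be biased.

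**What to change.** In section 9.0, name the analysis: a repeated-measures mixed model on the within-patient difference in PAHPI between the treated and vehicle sides at weeks 4, 8 and 12. Use visit as a factor, the baseline side difference by visit as covariate, and an unstructured covariance with a small-sample degrees-of-freedom correction. State that the week-12 contrast is the primary result and that every patient with at least one follow-up score is included.

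Keep 25 patients, but rewrite the power statement for this paired analysis. Give the assumed side difference and its SD, and the resulting power at 25 and at 20 to 22 evaluable pairs. Do not carry over the 80% from the z-test, which the stated inputs do not reproduce.

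Cost: wording in section 9.0 and a slightly more complex model, with no extra visits or patients. The benefit is modest, and the stated power will probably look less favourable. Keeping 25 discloses the effect of loss but does not offset it.

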## 10.0 Privacy/Confidentiality Issue

Data will be tabulated on a password-protected excel sheet stored on the principal investigator's computer. This computer will be stored in the WSUPG Department of Dermatology. All patients will be de-identified and labeled using a coding system (001, 002, etc).

Patients will have photographs taken of lesions at each visit. Photographs may be used in publications or presentations. Full-face photographs will be taken, an attempt will be made to de-identify the photograph as much as possible, including a black box over any distinguishing features.

## 11.0 Follow-up and Record Retention

Each participant will be enrolled in the study for 12 weeks with a total of 3 clinic visits. During these 12 weeks, the clinic visits include: 1 visit for initial baseline evaluation, and three follow-up appointments at 4 weeks, 8 weeks and 12 weeks of treatment. All pictures will be stored

securely on the dermatology department password protected hard drive and all data will be deleted at the end of the study.

